## Department of Medicine/Endocrinology

Email:

Phone:

38        **Abstract:**  
39  
40        Basal-bolus insulin therapy is recommended for patients with poorly controlled type 2  
41        diabetes and HbA1c >9%. However, basal-bolus insulin is labor intensive and associated with  
42        increased risk of hypoglycemia, glycemic variability, weight gain and poor compliance. Thus,  
43        there is a critical need for a simpler treatment regimen that could overcome these limitations.  
44        IDegLira, a fixed-ratio combination (FRC) therapy consisting of insulin degludec and liraglutide,  
45        is an attractive option for this population given its proven benefits on glycemic control, weight  
46        and compliance. *Accordingly, we propose a prospective randomized controlled trial comparing*  
47        *IDegLira and basal-bolus insulin therapy in achieving glycemic control (efficacy end-point), while*  
48        *preventing hypoglycemia and reducing glycemic variability and weight gain (safety end-point) in*  
49        *patients with uncontrolled T2D and HbA1c between ≥ 9-15%.* This study aims to show that a  
50        simpler regimen using a novel FRC agent (IDegLira) can improve glycemic control, decrease  
51        hypoglycemia, reduce the burden of diabetes care, and improve satisfaction/adherence in  
52        patients with poorly controlled T2D with HbA1c between ≥ 9-15%. This open-label, treat-to-  
53        target, two-arm parallel, controlled trial will randomize (1:1 ratio) patients with T2D and HbA1c ≥  
54        9%, treated with oral antidiabetic agents and/or basal insulin therapy (TDD ≤50 units), to  
55        IDegLira or basal-bolus insulin for 26 weeks. We will recruit a total of 150 patients from  
56        participating institutions. We anticipate recruiting 3-4 patients per week for a total recruitment  
57        period of approximately 12 months.

58

59      **BACKGROUND:**

60

61      Extensive literature from landmark studies have shown that persistent hyperglycemia is  
62      associated with short- and long-term complications. The UKPDS study, the largest study in  
63      patients with type 2 diabetes, showed that intensive glycemic control can reduce the risk of  
64      microvascular complications. Sustained hyperglycemia, also known as glucotoxicity, leads to  

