92 ***glycemic control, as measured by change in HbA1c (non-inferiority limit of 0.4%),***  
93 ***compared to treatment with basal-bolus insulin regimen in patients with poorly***  
94 ***controlled T2D (HbA1c  $\geq$ 9-15%).***

- 95 - Primary outcome: change in HbA1c from baseline after 26 weeks of treatment with  
96 IDegLira vs basal-bolus insulin (with metformin, unless contraindicated).
- 97 - **Hypothesis:** After 26 weeks of treatment, IDegLira will result in similar improvement in  
98 glycemic control compared to basal-bolus insulin therapy.

99 **Specific Aim 2:**

100 ***2. To determine whether treatment with IDegLira will result in lower rate of***  
101 ***hypoglycemic events and less glycemic variability (superiority), as measured by***  
102 ***continuous glucose monitoring (CGM), compared to basal-bolus insulin in patients***  
103 ***with T2D and HbA1c  $\geq$ 9-15%.***

- 104 - Patients with poorly controlled T2D randomized to IDegLira or basal-bolus (with  
105 metformin, unless contraindicated) will have a one-week blinded CGM study performed  
106 during follow-up visits at 1, 12, and 26 weeks as well as 8-point self-monitored blood  
107 glucose (SMBG). CGM will allow better detection of hypoglycemic events, particularly  
108 asymptomatic and nocturnal hypoglycemia. It will also provide critical information on  
109 time in glycemic range and glycemic variability.
- 110 - **Hypothesis:** IDegLira will result in less hypoglycemia and glycemic variability  
111 compared to basal-bolus insulin regimen.

112 **Specific Aim 3:**

113 ***3. To determine whether treatment with IDegLira will result in improved patient***  
114 ***satisfaction compared to treatment with basal-bolus in patients with T2D and high***  
115 ***HbA1c ( $\geq$ 9-15%).***

- 116 - Patients with poorly controlled T2D randomized to IDegLira or Basal-Bolus will  
117 complete the Diabetes Treatment Satisfaction Questionnaire (DTSQ) and Treatment-  
118 related impact measures for diabetes (TRIM-D) survey during follow-up visits.
- 119 - **Hypothesis:** Use of IDegLira is associated with higher patient satisfaction and  
120 adherence compared to a multiple-daily injection regimen with basal-bolus insulin.

122 **CURRENT STATUS OF WORK IN THE FIELD**

123 **Epidemiology and treatment of patients with poorly controlled T2D and HbA1c >9%**

124

125

126       Based on NHANES data from 2007-2010, up to   135   with Diabetes: US and Emory Data

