271                   (responder’s rate)
- 272                   • Percent of patients reaching A1c  $< 7.5\%$  without weight gain and no hypoglycemia”
- 273                   • Percent of patients with A1c  $> 10\%$  and  $> 11\%$  that achieve A1c  $< 7.5\%$  and  $< 8\%$

- Percent of patients with HbA1c <7.0% at 26 weeks and no weight gain
- Percent of patients with HbA1c <7.0% at 12 weeks and no hypoglycemia
- Incidence of documented symptomatic hypoglycaemia, defined as an event with typical symptoms of hypoglycaemia accompanied by SMBG or CGM (<70 mg/dL and < 54 mg/dL) that occurs at any time of the day
- Incidence of asymptomatic hypoglycaemia, defined as no typical symptoms reported by the subject but detected by SMBG or CGM (<70 mg/dL and < 54 mg/dL)
- Incidence of severe hypoglycaemia, defined as severe cognitive impairment requiring assistance from another person
- Incidence of nocturnal symptomatic hypoglycaemia, defined as an event with typical symptoms of hypoglycaemia accompanied by SMBG or CGM <70 mg/dL and < 54 mg/dL that occurs between 00:00 and 05:59 hrs
- Incidence of nocturnal asymptomatic hypoglycaemia, defined as SMBG or CGM <70 mg/dL and < 54 mg/dl between 00:00 and 05:59 hrs
- Percentage of time below 70 mg/dL and <54 mg/dl as obtained by CGM
- Percentage of time in range (BG 70-180) as measured by CGM
- Glycemic variability, as measured by SD (standard deviation), %CV (coefficient of variance), Mean Amplitude Glucose Excursions (MAGE)
- Patient satisfaction and quality of life, as measured by the DTSQ and T R I M - D questionnaires
- Number of emergency room visits and hospital readmissions
- Change from baseline in total insulin dose (units/day)
- Number of treatment emergent AE

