## 300 **STUDY DESIGN AND METHODS:**

301 The study is a 26-week, open-label, treat-to-target, two-arm parallel, randomized, controlled trial  
302 investigating the efficacy and safety of IDegLira versus basal-bolus insulin in patients with T2D.  
303 Patients with HbA1c  $\geq$  9% treated with oral antidiabetic agents and/or basal insulin therapy  
304 (TDD  $\leq$  50 units) will be randomized in a 1:1 manner to receive IDegLira or basal-bolus insulin  
305 regimen (plus metformin unless contraindicated), as shown in Fig 2. Subjects will have contact  
306 with the study team via clinic visits or phone contacts for a total of 29-weeks, as shown in the  
307 figure below (Fig 2 and Table 1).

308  
309 Figure 2. Study design

311 Legend: OAD: Oral anti-diabetic agents, EOT: End-of-treatment, FUP: Follow-up safety visit

312  
313 Visits will be distributed as follows: initial screening visit/CGM insertion (visit 1), 2 weeks of  
314 screening/run-in period, randomization visit (visit 2), 26-week treatment period (visits 4-18), and  
315 a follow-up safety visit after the end the 26-weeks treatment period (visit 19). Subjects will have  
316 contact with the study team via clinic visits or phone contacts for a total of 9 clinic visits and 9  
317 telephone contacts. This study will include patients with a known history of T2D, age 18-80,  
318 treated with oral antidiabetic agents including metformin, sulfonylurea, repaglinide/nateglinide,  
319 pioglitazone, DPP4 inhibitors, SGLT2 inhibitors, (monotherapy + basal insulin) or in combination  
320 therapy (2-3 agents), and/or on basal insulin at a total daily dose (TDD) of  $\leq 50$  units.

321 Participants previously using basal insulin [neutral protamine hagedorn (NPH), mixed insulin,  
322 detemir or glargine insulin], will be switched to study-provided Degludec or IDegLira and/or  
323 Aspart pens. Metformin will be continued at same dose during the study, unless contraindicated.  
324 Patients previously treated ambulatory with basal-bolus insulin therapy and/or GLP1-RA will be  
325 excluded. Patients transiently treated with basal-bolus insulin (standard-of-care treatment)  
326 during hospital admission can be included. Recommendations on insulin adjustment will be  
327 provided at each visit or phone encounter by a study physician.

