### 328 329 **Rationale for study design**

330 Based on the DUAL trial program, a total of 26 weeks of treatment is sufficient to reach  
331 stable HbA1c levels, with a minimum of 12 weeks in the maintenance period. This timeline has  
332 been previously shown to be sufficient to collect data for efficacy and safety. A parallel design  
333 will allow for assessment of efficacy and safety in the shortest time in each group, compared to  
334 a cross-over design. An open label design allows us to use a simpler regimen with a single  
335 injection of IDegLira, as blinding the subjects will require a double dummy design with three  
336 extra subcutaneous injections per day, thus imposing a high burden on subjects, thereby  
337 increasing the non-compliance and withdrawal rates. Patients in both arms will  
338 receive the same degree of self-monitoring and follow-up. Patients will have

339 blinded CGM to avoid the bias of glycemic improvement by using real-time glucose  
340 data from CGM. The primary endpoint will use HgA1c changes, a standard  
341 laboratory test shown to correlate with risk of diabetes complication, thus limiting  
342 the assessment bias. Secondary endpoints will include rates of asymptomatic  
343 hypoglycemia or nocturnal hypoglycemia as detected by CGM, which will typically  
344 not be detected by the standard-of-care SMBG.

345

346 Table 1- Schedule of events during the study period

Visit # (V) Phone visit (P)	V1*	V2*	P3*	P4*	P5*	V6*	P7*	P8*	P9*	V10**	P11**	V12**	V13**	P14**	V15**	P16**	V17**	V18**
Time-wks	-2	0	1	2	3	4	5	6	7	8	10	12	14	16	20	24	26	27
Inf. Consent		X																
Inc/exclusion	X	X																
Rando@		X																
Withdrawal cx		X	X	X	X	X	X	X	X	X	X	X	X	x	X	x	x	
Drug compl		X				X				X		X	X	x		X	x	
Dose adjust			X	X	X	X	X	X	X	X	X	X	X	x	X	X	x	
Efficacy																		
Vital signs@	X	X				X				X		X	x		x	X	x	
Phys exam	x																	
Pregnancy test*	X	X				X				X		X					X	
Body Measurements	X	X				X				X		X	X		x		X	
BMI	X	X				X				X		X	x		x			
HbA1c	x											X					X	
CMP	X&											X					X	
Fasting glucose&		X				X				X		X				X	x	
Instruct 8-p SMBG	x				X						X					X		
Collect 8-pt SMBG		X				X						X					X	
Labs	X^																X^*	
7d-CGM insert	X 											X					X	
7d- CGM collect	x											x					x	
DTSQ&TRIM-D		X										X					X	
Safety																		
Adverse events			X	X	X	X	X	X	X	X	X	X	x	X	X	X	X	
Hypoglycemia			X	X	X	X	X	X	X	X	X	X	x	X	X	X	X	

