746           • HbA1c, Fasting Glucose/CMP and pregnancy test (WOCP per PI discretion) will be  
747            obtained

748           • CGM will be inserted

749           • Patients will complete the DTSQ and TRIM-D questionnaires

750           • AE and hypoglycemia data will be collected, as well as concomitant medications.

751           • Drug dispensing

752

753           **CGM visits (insertion on weeks -2, 12, 26 and collection on week 0, 14, 27)**

755           All enrolled participants will have a blinded/professional CGM study performed during  
756           week -2, 12, and 26 weeks of follow-up.

757           During this visit, participants will receive training on CGM use and reinforce SMBG diary  
758           collection. Trained personnel will proceed with sensor insertion, transmitter placement and  
759           hook-up. After that, the transmitter will be activated, the CGM session will be started.

760           After 7 days, subjects will remove the sensor and return to the scheduled visit. Transmitter  
761           will be connected to the computer for data downloading. CGM summary will be reviewed to  
762           determine the quality.

763           Sensor will be stored following standard precautions. Onsite visits will be allowed for upload of  
764           the study devices and face-to-face discussion about hypoglycemia and hyperglycemia

765 episodes, insulin doses, AE/SAE evaluation, and replacement of study medication, if required.  
766 Trained personnel will input required clinical and demographic data into the sensor database  
767 software. Subjects will complete an 8-point SMBG for 1 day (as shown in Table 1) prior to clinic  
768 visit. Subjects will bring their glucose meter, CGM sensor (if applicable), BG diary, to each  
769 onsite visit.

770 **Visit 17 (Week 26, end-of-study)**

- 771 • Diabetes Treatment Satisfaction Questionnaire Status (DTSQs) and TRIM-D survey
- 772 • Blood sampling as indicated on page 12- schedule of events during the study period,  
773 including HbA1c assessment to determine efficacy of treatment
- 774 • Study diaries collected and reviewed for BG levels, episodes of hypoglycemia, insulin  
775 self-administration

776

777 **Visit 18 (week 27, case sign-off)**

- 778 • This visit should occur at least one week after the last treatment visit
- 779 • Since degludec has a prolonged duration of action, this visit will serve to monitor for  
780 adverse events.

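### The third CGM wear runs from week 26 to week 27, after the planned 26 weeks of treatment, and the protocol does not say whether study drug continues during it

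*Combined protocol and SAP*

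**What the plan says.** All references are to the combined protocol and SAP.

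- **Treatment length.** The Abstract assigns patients to "IDegLira or basal-bolus insulin for 26 weeks". Study Design and Methods gives clinic or "phone contacts for a total of 29-weeks".
- **CGM timing.** The CGM visits section is the most explicit: "insertion on weeks -2, 12, 26 and collection on week 0, 14, 27". The Visit 18 list has the sensor coming out after 7 days. Other places are looser. Specific Aim 2 puts CGM "during follow-up visits at 1, 12, and 26 weeks", Assessments for Safety names weeks -1, 12 and 26, and the Table 1 row "7d- CGM collect" carries its last mark under V17 rather than V18.
- **Data used.** Under Definitions, CGM data from the first day after insertion are not analysed.
- **Outcomes that depend on it.** The secondary outcomes include "Percentage of time below 70 mg/dL and <54 mg/dl as obtained by CGM" and "Percentage of time in range (BG 70-180) as measured by CGM", together with glycaemic variability and CGM-detected hypoglycaemia. Specific Aim 2 is a superiority aim built on these CGM measures.
- **End of treatment.** Visit 17 is labelled end-of-study. Visit 18 is labelled case sign-off, comes no sooner than a week after the final treatment visit, and is justified by degludec's long action. Study Design and Methods and Visit Procedures instead count visits 4 to 18 as treatment, followed by "a follow-up safety visit after the end the 26-weeks treatment period (visit 19").

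**The concern.** A week-26 CGM recording would ordinarily be read as the end-of-treatment comparison of the two regimens. Here the sensor goes in when the planned 26 weeks have just finished. If patients stop study drug at Visit 17, the recording reflects residual degludec plus whatever regimen follows, which the protocol does not specify. It could not then be read as IDegLira versus basal-bolus.

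There are only two post-baseline CGM windows, so this is one of two. It may also be the more informative one. The design rationale expects at least 12 weeks of maintenance, so maintenance should begin by week 14 (26 - 12), and the week-12 wear may come before that. Because the last dose is undefined, two sites could handle the week differently and both be following the protocol.

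**Working it through.** **1. Reproduce the plan's own counts.**

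- Contact time: week -2 to week 27 is 27 + 2 = 29 weeks, which matches the stated 29. It splits as 2 run-in + 26 treatment + 1 follow-up.
- Contacts in Table 1: V1, V2, V6, V10, V12, V13, V15, V17, V18 = 9 clinic; P3, P4, P5, P7, P8, P9, P11, P14, P16 = 9 phone. The total of 18 matches the text. There is no nineteenth contact, so the Visit 19 in the narrative does not exist in the schedule.

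**2. Place the third wear on the calendar (randomisation = day 0).**

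- Planned treatment: 26 × 7 = 182 days.
- Sensor in at week 26 = day 182; sensor out at week 27 = 27 × 7 = day 189.
- First 24 hours dropped: analysable span is day 183 to day 189, which is 6 days.
- Analysable days on or before day 182: 0 of 6.

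**3. Allow for the Visit 17 window (±7 days, Table 1 footnote).** If Visit 17 is k days early, the analysable span is day 183 - k to day 189 - k. If drug continues to day 182, max(0, k - 1) of the 6 days fall within planned treatment: 0 for any k up to 1, 1 at k = 2, 3 at k = 4, 6 at k = 7. If drug stops at Visit 17 itself, the count is 0 for every k. These are calendar counts, not a measure of bias.

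**4. Set the statements on drug status side by side.**

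| Suggests drug has stopped | Suggests drug continues |
|---|---|
| Visit 18 follows the final treatment visit by a week or more | Study Design and Methods and Visit Procedures: visits 4 to 18 are treatment |
| Visit 18 is justified by degludec's prolonged action | Follow-up Visits (visit 6-18): doses adjusted and medication dispensed |
| Visit 17 is labelled end-of-study | Text after the Visit 18 list: insulin titrated at every visit |
| | CGM visits: medication can be replaced if needed; Table 1: dose adjustment marked at V17 |

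Neither column contains a last-dose date. The visits 4 to 18 wording is probably old numbering, because it needs a Visit 19 that the schedule lacks. Moving both numbers down by one (treatment to V17, follow-up at V18) agrees with the Visit 18 text.

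**5. Table 1 cells that decide nothing.** Dose adjustment is blank at V18, but so are adverse events and hypoglycaemia, although adverse-event monitoring is that visit's stated purpose. Dispensing has no mark after V12 (week 12), yet treatment plainly runs to week 26. The table's column alignment is also uncertain: End-of-Trial appears under V15 (week 20).

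**The case against.** The best case against is that the protocol twice describes visits 4 to 18 as the treatment period. Read literally, the wear ending at Visit 18 is then on treatment. The Visit 18 condition refers to a visit rather than a last dose, and the degludec sentence implies stopping without stating it. On this view the matter is a missing sentence.

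Part of this stands: the documents do not establish that drug stops at Visit 17. But the literal reading puts week 27 inside a 26-week period and leaves the safety visit with no slot in the schedule, so it does not settle the question. A schedule that can be followed as written and still give off-drug outcomes for Aim 2 needs more than tidying.

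Three stronger readings may tempt a reader, and the documents do not support them:

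- That the blank V18 cells or the absence of dispensing after V12 show that drug had stopped. For the reasons in the check, they are not evidence either way.
- That the schedule fails whichever way drug is handled. If drug continues, Visit 18 can still collect adverse events and the sensor; only its degludec rationale weakens.
- That hypoglycaemia as a whole is compromised. Assessments for Safety bases the safety endpoint on point-of-care glucose monitoring, and Table 1 marks hypoglycaemia collection at all 15 contacts from P3 to V17.

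**Conclusion.** The point holds in a limited form. On the nominal schedule, 0 of 6 analysable days of the third CGM fall within planned treatment, and drug status in that week is undefined, with text pointing both ways. If drug stops at Visit 17, one of the two post-baseline CGM windows is off treatment, and the week-26 time below range, time in range, variability and CGM-detected hypoglycaemia do not compare the randomised regimens. The documents give no basis for sizing the dilution, and there is none if drug continues to sensor removal.

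This assumes that the CGM visits and Visit 18 text, the most explicit on timing, governs over the looser statements elsewhere, and that Visit 17 is not more than a day early. The primary HbA1c endpoint, the week-12 CGM, and SMBG or reported hypoglycaemia through week 26 are untouched. It would go too far to call Aim 2 invalid. This is a cheap improvement to make, with medium confidence that the wear would in practice be off drug.

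**What to change.** Choose one of two changes.

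**(a) Move the wear before Visit 17.** Insert the third sensor 7 to 10 days before the booked Visit 17, collect it at Visit 17, and state that study drug continues to Visit 17. The analysable span then runs from 6 to 0 days before Visit 17 (insertion 7 days ahead) through 9 to 3 days before (insertion 10 days ahead), so 6 of 6 days are on drug. Make the week-24 phone contact a clinic visit at about week 25. If the week-27 safety visit becomes a phone call, contacts stay at 9 clinic and 9 phone. Cost: the in-person safety visit is lost, and the gap after V15 (week 20) grows from 4 weeks to about 5. Keeping the safety visit in clinic gives 10 clinic and 8 phone contacts, still 18.

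**(b) Keep the wear and extend drug.** State that randomised drug is dispensed and continued until sensor removal at week 27, and place the post-treatment safety contact by phone at least a week later. Cost: one more week of study drug, one more phone contact (18 + 1 = 19), and contact time of at least 28 + 2 = 30 weeks.

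Neither option needs an extra sensor. Both need Table 1 and the CGM, Visit 17 and Visit 18 text amended, and the visit numbering in Study Design and Methods and Visit Procedures made consistent. In both cases record the last-dose date. Label any wear already done after drug stopped as post-treatment, with week 12 as the on-treatment CGM time point for those patients.

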Trial material																		
Drug dispensing		X				X				X		X						
Drug account			X		X					X		X				x		
End-of-Trial															x			

391 \*+/- 3 days. \*\*+/- 7 days. Labs: ^ pregnancy test, ketones, lipid panel^\* and GAD65 (If concern for Type 1 diabetes, GAD65 and ketones  
392 will be ordered during screening, per PI discretion). Pregnancy test for WOCP as deemed by investigator & fasting defined as at least 8  
393 hours without food or drinks or diabetes medications, except water and other prescribed medications.  +/- 7 days, but before  
394 randomization visit. Fasting glucose could be obtained from a chemistry sample obtained during the visit or POC BG. Body  
395 measurement includes: weight, height and waist and hip circumference. @ During "randomization" and "vital signs" visits, subjects will  
396 receive training on device use.

397 **Treatment of subjects:**

398 **Group 1) IDegLira Group**

399 • Discontinue OADs (SU, DPPIVi, glinides, and pioglitazone), except metformin  
400 (unless contraindicated) and SGLT2i.

401 • Start IDegLira at 16 dose steps (degludec 16 units/liraglutide 0.6 mg), per U.S  
402 labeling indications and/or provider discretion.

403 • IDegLira will be given once daily, at the same time of the day with or without food.

404 • IDegLira will be titrated until the maximum dose (50 steps) is reached, up to target fasting  
405 BG between 70 and 100 mg/dl (Treat-To-Target Trial protocol), see algorithm below.

406 • Titration will occur twice a week: 1) self-titration by patients once a week and 2) phone call/  
407 contact by research team once a week, for the initial 8 weeks. After that, patients will self-  
408 titrate study medications per dosing algorithm.

409 • IDegLira will be titrated by 2-step-dose increment (2 IU of degludec and 0.072 of liraglutide),  
410 to a maximum of 8 steps per week.

411 • The maximum allowed dose of IDegLira 50 dose steps provide 50 U of degludec and 1.8mg  
412 of liraglutide.

413 • Titration will be performed twice weekly (every 3 to 4 days) based on the previous self-  
414 monitored fasting (pre-breakfast) BG measurement (mean of 3 consecutive days). Patients  
415 will be provided with self-titration algorithms for insulin adjustments.

416 • Subjects not at goal (fasting or mean SMBG from 3 consecutive days > 300 mg/dl) requiring  
417 > 50 dose steps of IDegLira, will be considered “treatment failures”. Degludec will be added  

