418 to IDegLira as “rescue” basal insulin therapy. The dose of IDegLira will remain unchanged.

419 • The dose of “rescue” Degludec will be recorded and titrated twice weekly to target FPG of  
420 70-100 mg/dl, per provider discretion, as shown below.

Titration algorithm for IDegLira and Degludec pens	Insulin dosage IU/d)*
$\geq 181$	8
141-180	6
121-140	4
101-120	2
71-100	no adjustments
$<70$	-2 If dose $> 45$ U/d, decrease by 10%
$<56$	-4 If dose $> 45$ U/d, decrease by 10%

\* Maximum titration dose per week: 8 units

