#### Group 2: Basal-Bolus Insulin Group (Begin BB trial)

- Discontinue OADs (SU, DPPIVi, glinides, and pioglitazone), except metformin (unless contraindicated) and SGLT2i.
- Insulin naïve participants will start at a daily dose of 10 units of degludec U-100 (or 0.2 u/kg/d per investigator discretion).
- Participants previously using basal insulin [neutral protamine hagedorn (NPH), mixed insulin, detemir or glargine U100] will be switched to study-provided degludec pens.
- For participants taking basal insulin prior to randomization, the conversion dose is 1:1 unit. The total daily basal dose could be the same or reduced by 20% at the investigator's discretion.
- Titration will be performed twice weekly based on the previous self-monitored fasting (pre-breakfast) BG measurement (mean of 3 consecutive days). Titration will occur as follows: 1) self-titration by patients once a week and 2) phone call/ contact by research team once a week, for the initial 8 weeks. After that, patients will self-titrate study medications per dosing algorithm.
- Degludec will be given once daily at the same time, and titrate up to fasting blood glucose 70-100 mg, with no maximum dose.
- Basal insulin should be adjusted before adjusting pre-meal aspart, as shown below.

448 **Degludec U100 Insulin adjustment**

449

Mean fasting BG from preceding 3 days (mg/dl)	Insulin dosage IU/d)
>181	8
141-180	6
121-140	4
101-120	2
71-100	no adjustments
<70	-2 If dose > 45 U/d, decrease by 5%
<56	-4 If dose > 45 U/d, decrease by 10%

450

451

452 **Aspart Insulin dosage:**

453 • Aspart will be given before meals, to target pre-meal BG < 70-100 mg/dl.

454 • At the start of the trial, participants will be prescribed 4 U insulin aspart before the  
455 largest/main meal or; before each main meal (3 typical large meals per day:  
456 breakfast, lunch, and dinner,  $\leq$ 4 times per day) per investigator discretion.

457 • For insulin naïve participants or per investigator discretion, total aspart dose will  
458 calculated at 0.2 u/kg/d, and equally divided in three doses to be started before the  
459 main/largest meal or before each meal (3 typical large meals per day: breakfast,  
460 lunch, and dinner,  $\leq$ 4 times per day), per investigator discretion.

461 • If patients are started on only one dose for the largest meal, a second and third dose  
462 may be added, as detailed above. Subjects will be provided with titration algorithms.

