- 781 • Sensor removal (after 7 days).

782 During each visit, participants will have their insulin dose titrated to achieve a fasting  
783 glucose 70-100 mg/dL as detailed in the insulin titration algorithm. Once the fasting glucose 3-  
784 day average is <100 mg/dL, insulin doses will be kept constant, unless the participant  
785 experiences recurrent or severe hyperglycemia.

786  
787  
788  
789  
790

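### The closing titration sentence holds insulin at any 3-day fasting mean below 100 mg/dL, and so conflicts below 70 mg/dL with the dose cuts in both basal tables (minor wording inconsistency)

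*Combined protocol and SAP*

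**What the plan says.** Two consecutive sentences close the visit descriptions. The first says that at each visit the dose is titrated towards fasting "glucose 70-100 mg/dL as detailed in the insulin titration algorithm". The second is the hold rule. Once the fasting 3-"day average is <100 mg/dL, insulin doses will be kept constant, unless the participant" "experiences recurrent or severe hyperglycemia". That is its only exception.

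Under Treatment of subjects, each arm has a basal table.

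- **Group 1 (IDegLira, and rescue degludec).** The text above the table bases titration on "monitored fasting (pre-breakfast) BG measurement (mean of 3 consecutive days). Patients" (the last word opens the next sentence). The table makes no change at 71-100 mg/dL. Below 70 it takes off "2 If dose $> 45$ U/d, decrease by 10" per cent, and below 56 it takes off "4 If dose $> 45$ U/d, decrease by 10" per cent.
- **Group 2 (basal-bolus degludec).** The table is headed "Mean fasting BG from preceding 3 days (mg/dl"). It also makes no change at 71-100. Below 70 it takes off "2 If dose > 45 U/d, decrease by 5" per cent. Below 56 it takes off 4 units, or 10 per cent above 45 U/d.

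Three other places deal with low glucose. The section on time-points for the 8-point SMBG profile has values under 70 mg/dL trigger an intervention. Protection against Risks reduces basal insulin after hypoglycemia and points to the algorithm. Precautions/Over-dosage adjusts insulin for hypoglycemic values by a predefined algorithm.

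**The concern.** The hold sentence and the two tables are driven by the same quantity, so they can be compared directly, and below 70 mg/dL they give different instructions. The hold sentence comes straight after the reference to the algorithm and says what to do once a threshold is crossed. Staff could therefore take it as the more specific rule.

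What is at stake is patient safety at the level of a single dosing decision. Someone who follows the sentence literally would keep a basal or IDegLira dose that the table reduces, in a participant whose average fasting glucose is already low. Hypoglycemia is the safety endpoint under Assessments for Safety and part of Specific Aim 2, so the rule for responding to it should be unambiguous.

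**Working it through.** The plan gives no figure on this point to reproduce. The check sets the two rules side by side and then sizes the difference.

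**Step 1: same metric.** The hold sentence uses the 3-day fasting average. The Group 1 text and the Group 2 table heading use the mean fasting value over three days. The comparison is like with like.

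**Step 2: action under each rule, dose up to 45 U/d.** A mean below 56 is taken to follow the below-56 row only.

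| 3-day fasting mean (mg/dL) | Hold sentence, literal | Basal tables, both arms | Agree? |
|---|---|---|---|
| 50, 55 | constant | −4 units | no |
| 56, 60, 65, 69 | constant | −2 units | no |
| 70 | constant | no row | table silent |
| 71, 85, 99 | constant | no adjustment | yes |
| 100 | not triggered | no adjustment | yes |

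The conflict is confined to means below 70. A mean of exactly 70 falls between the no-adjustment row (71-100) and the below-70 row.

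**Step 3: size of the withheld cut.** Assumption: above 45 U/d the percentage replaces the unit step. The cut is then percentage × current dose. The hold sentence read literally gives 0 in every row.

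| Mean | Current dose | IDegLira/rescue degludec table | Basal-bolus degludec table |
|---|---|---|---|
| below 70 | up to 45 U/d | 2 | 2 |
| below 70 | 46 U/d | 0.10 × 46 = 4.6 | 0.05 × 46 = 2.3 |
| below 70 | 50 U/d | 0.10 × 50 = 5.0 | 0.05 × 50 = 2.5 |
| below 56 | up to 45 U/d | 4 | 4 |
| below 56 | 46 U/d | 0.10 × 46 = 4.6 | 0.10 × 46 = 4.6 |
| below 56 | 50 U/d | 0.10 × 50 = 5.0 | 0.10 × 50 = 5.0 |

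IDegLira is capped at 50 dose steps. Basal-bolus degludec has no maximum dose, so 46 to 50 U/d is only an illustration in that arm and the percentage cuts grow with the dose.

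**Step 4: frequency.** The documents do not say how often a 3-day fasting mean below 70 is expected, so neither patients nor occasions can be counted.

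**The case against.** The best defence is that the sentence should be read with the one before it. That sentence sets a 70-100 mg/dL target and defers to the algorithm. A mean of 65 is off target, and the algorithm says to cut. Since the only exception is hyperglycemia, which is a reason to resume increases, the hold can be read as a stop on up-titration that leaves reductions to the tables. The three other provisions on low glucose point the same way. The working rules are the arm-specific tables: participants self-titrate from them, and Study Design and Methods has a study physician advise on dose at every visit or call. A physician who held the dose at a mean of 50 would have to disregard several instructions.

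Most of this stands. It shows what the sponsor very probably means and that practical exposure is limited. It does not make the text consistent, because keeping a dose constant excludes lowering it as well as raising it.

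A reader might infer more than the documents support:

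- **That hyperglycemia is a misprint for hypoglycemia.** This is possible but unconfirmed. Changing that word alone would also not be enough, because a first, non-severe mean of 65 would still be held.
- **That exposure is bounded by Table 1.** It marks dose adjustment at 15 contacts (P3 to V17: 6 clinic, 9 telephone). This is not a strict ceiling, because the CGM visits section allows other onsite visits, and it says nothing about how often the mean is low.
- **That the arms are treated unequally.** Above 45 U/d the below-70 cut is 10 per cent in one table and 5 per cent in the other. The hold sentence applies to both arms, and nothing shows that it would be followed literally more often in one of them.

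**Conclusion.** Wrong as written, and minor. It is an internal inconsistency in a dosing rule. Read literally, the hold sentence contradicts the reduction rows of both basal tables at every 3-day fasting mean below 70 mg/dL and nowhere else. The withheld cut is 2 or 4 units up to 45 U/d, and 2.3 to 5.0 units at 46 to 50 U/d, assuming that the percentage replaces the unit step above 45 U/d.

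Confidence is high about the literal wording. It does not extend to a claim that the sponsor means to withhold reductions, because the preceding sentence and the three safety provisions make the intention to reduce recoverable. Nor does the point question the treat-to-target design. No bias between arms and no effect on sample size, power or alpha is shown.

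**What to change.** Replace the hold sentence with wording such as: *Once the 3-day fasting mean lies within 70-100 mg/dL, the basal insulin or IDegLira dose is held; a mean below 70 mg/dL follows the below-70 and below-56 reduction rows of the basal titration table for that arm.* Naming basal insulin or IDegLira limits the rule to the doses that the fasting mean drives, since aspart has its own table based on pre-prandial and bedtime values.

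The sponsor should also confirm whether hyperglycemia in the exception is intended. As a tidy-up, label the no-adjustment row 70-100 in both basal tables, so that a mean of exactly 70 has an action.

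The cost is one sentence and one row label in each of two tables. No patients, visits or analyses change.
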